3.13 Measurable disease as defined in section 11.0

3.14 Provide written informed consent.

3.15 Patient must be considered for treatment with an IMiD containing regimen.

3.16 ECOG Performance Status (PS) 0, 1, 2 or 3 (Appendix I).

3.17 The following laboratory values obtained \leq 14 days prior to registration:

- Hemoglobin \geq 7.0 g/dL
- Absolute neutrophil count (ANC) \geq 1000/mm³
- Platelet count \geq 50,000/mm³

- Total bilirubin $\leq 1.5 \times$ upper limit of normal (ULN) unless due to Gilbert's syndrome, in which case the direct bilirubin must be $\leq 1.5 \times$ ULN.
- Alanine aminotransferase (ALT) and aspartate transaminase (AST) $\leq 3 \times$ ULN ($\leq 5 \times$ ULN for patients with liver involvement)
- PT/INR/aPTT $\leq 1.5 \times$ ULN OR if patient is receiving anticoagulant therapy and INR or aPTT is within target range of therapy
- Calculated creatinine clearance ≥ 45 ml/min using the Cockcroft-Gault formula below:

Cockcroft-Gault Equation:

$$\text{Creatinine clearance for males} = \frac{(140 - \text{age})(\text{weight in kg})}{(72)(\text{serum creatinine in mg/dL})}$$

$$\text{Creatinine clearance for females} = \frac{(140 - \text{age})(\text{weight in kg})(0.85)}{(72)(\text{serum creatinine in mg/dL})}$$

3.18 Negative pregnancy test done ≤ 7 days prior to registration, for persons of childbearing potential only.
NOTE: If the urine test is positive or cannot be confirmed as negative, a serum pregnancy test will be required.

3.19a Willing to return to enrolling institution for follow-up (during the Active Monitoring Phase of the study).

3.19b Willingness to provide mandatory blood and bone marrow specimens for correlative research (see Section 14.0).

3.19c Willing to follow the requirements of the Pomalyst® REMS program

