4.0 Test Schedule

Tests and procedures	Active Monitoring Phase					
	Prior to registration		Prior to Day 1 Cycle 1	Prior to Day 1 Cycle 2	Prior to Day 1 Cycles 3-6	End of Treatment
	≤28 days	≤14 days				
Window				±3 days	±3 days	±7 days
Complete Medical History		X				
Physical exam, Wt, PS		X	X ³	X	X	X
Adverse event assessment		X		X	X	X
Pregnancy test ¹		X				
Height		X				
Hematology group: CBC with 5-part differential		X	X ³	X	X	X
Chemistry group to include serum creatinine, calcium, T.Bili, D. bili, AST, and ALT		X	X ³	X	X	X
LDH, Beta-2-microglobulin, Plasma cell assessment		X	X ³			
PT/PTT/INR		X				
TSH		X				
Electrophoresis of serum and urine		X	X ^{3,5}	X ⁵	X ⁵	X ⁵
Immunofixation or mass fixation of serum and urine		X		X ⁷	X ⁷	X ⁷
Affected Serum Immunoglobulin ²		X	X ³	X	X	X
Serum Immunoglobulin free light chain		X	X ³	X	X	X
WBLDCT ³ or PET/CT	X			X ³	X ³	
Bone marrow aspirate and biopsy	X					
Patient Medication Diary (Appendix II)			X	X	X	
Research bone marrow sample ^R	X			X ⁶		X ⁴
Research blood sample ^R	X			X ⁶		X ⁴

Cycle 1 = 21

Cycles 2-6 = 28 days

Footnotes on following page:

1. For women of childbearing potential only. Must be done ≤ 7 days prior to registration. If the urine test is positive or cannot be confirmed as negative, a serum pregnancy test will be required
2. Affected immunoglobulin refers to the baseline M-protein type, that is, IgG, IgA, or IgD. Not applicable if patient “non-secretory” or if patient has no heavy chain, i.e. light chain myeloma. Affected immunoglobulin is required after baseline only if it used for disease monitoring instead of SPEP (e.g. IgA myeloma).
3. Baseline then only if clinically indicated.
4. Optional BM sample submission for patients who discontinue treatment due to disease progression or relapse, intolerable AEs, patient refusal, subsequent treatment for myeloma.
5. Urine Electrophoresis required only if used to assess disease response
6. Bone marrow aspirate done at the end of Cycle 1 (prior to cycle 2) will be paid for by research.
7. Immunofixation (IF) only needed in absence of M-Spike to document CR or SCR

R Collected as part of the IRB# 521-93, IRB# 14-009163 and/or IRB# 919-04

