6.5 Treatment start

Treatment cannot begin prior to registration and must begin ≤ 28 days after registration.

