7.0 Protocol Treatment

7.1 Treatment Schedule

Cohort A and B Cycle 1

Treatment medication table. Patient may receive Lenalidomide OR Lenalidomide + Dexamethasone.

Agent	Dose Level	Route	Day	Re Rx
Lenalidomide	25 mg*	Oral	Cycle 1: Day 1-14	Cycle 1: 21 days
Dexamethasone	40 mg**	Oral	Cycle 1: Day 1 ,8, ,15	Cycle 1: 21 days

Cycle 1 length = 21 days

* Starting dose will be determined as per the creatine clearance below (see 7.12)

**The dose of dexamethasone used can be determined by the treating physician and omitted if needed.

Cohort C and D Cycle 1

Treatment medication table. Patient may receive Lenalidomide + Dexamethasone OR Pomalidomide + Dexamethasone.

Agent	Dose Level	Route	Day	ReRx
Lenalidomide	25 mg*	Oral	Cycle 1: Day 1-14	Cycle 1: 21 days
Pomalidomide	4 mg	Oral	Cycle 1: Day 1-21	Cycle 1: 21 days
Dexamethasone	40 mg**	Oral	Cycle 1: Day 1 ,8, ,15	Cycle 1: 21 days

Cycle 1 length = 21 days

* Starting dose will be determined as per the creatinine clearance below (see 7.12)

** The dose of dexamethasone used can be determined by the treating physician and omitted if needed.

Cohort A and B Cycles 2-6

Treatment Medication Table. Patient may receive Lenalidomide based regimens.

Agent	Dose Level	Route	Day	Re Rx
Lenalidomide	25 mg*	Oral	Cycle 2-6: Day 1-21	Cycles 2-6: 28 days
Dexamethasone	40 mg**	Oral	Cycle 2-6: Day 1 ,8, ,15, 22	Cycles 2-6: 28 days

Note: Standard of care agents can be added for cycles 2-6 as long as the regimen contains lenalidomide

Cycles 2-6 length = 28 days

* Any dose-adjustments will be determined as per the creatine clearance below (see 7.12).

** The dose of dexamethasone used can be determined by the treating physician and omitted if needed.

Cohort C and D Cycles 2-6

Treatment medication table. Patient may receive Lenalidomide based regimen OR Pomalidomide based regimen.

Agent	Dose Level	Route	Day	ReRx
Lenalidomide	25 mg*	Oral	Cycles 2-6: Day 1-21	Cycles 2-6: 28 days
Pomalidomide	4 mg	Oral	Cycles 2-6: Day 1-21	Cycles 2-6: 28 days
Dexamethasone	40 mg**	Oral	Cycle 2-6: Day 1,8,15,22	Cycles 2-6: 28 days

Note: Standard of care agents can be added for cycles 2-6 as long as the regimen contains lenalidomide or pomalidomide

Cycles 2-6 length = 28 days

* Any dose-adjustments will be determined as per the creatinine clearance below (see 7.12).

** The dose of dexamethasone used can be determined by the treating physician and omitted if needed.

7.12

Creatinine Clearance (CrCl)	Lenalidomide Dose

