15.1 Lenalidomide for Oral Administration (Revlimid®)

15.11 **Background:** Lenalidomide has antineoplastic, immunomodulatory and antiangiogenic characteristics via multiple mechanisms. Lenalidomide selectively inhibits secretion of proinflammatory cytokines (potent inhibitor of tumor necrosis factor-alpha secretion); enhances cell-mediated immunity by stimulating proliferation of anti-CD3 stimulated T cells (resulting in increased IL-2 and interferon gamma secretion); inhibits trophic signals to angiogenic factors in cells. Lenalidomide inhibits the growth of myeloma cells by inducing cell cycle arrest and cell death.

15.12 **Formulation and Dispensing:** Commercially available for oral administration as: Capsules: 5 mg, 10 mg, 15 mg and 25 mg

Lenalidomide is approved for marketing only under a FDA approved, restricted distribution program called RevAssist. Physicians, pharmacies, and patients must be registered; a maximum 28-day supply may be dispensed; a new prescription is required each time it is filled; pregnancy testing is required for females of childbearing potential.

15.13 **Preparation, storage, and stability:** Store oral capsules at controlled room temperature between 15°C and 30°C (59 °F and 86 °F). Refer to labeling on the bottle for expiration date of the commercial tablets.

15.14 **Administration:** Refer to the treatment section for specific administration instructions. Administer with water. Swallow capsule whole; do not break, open, or chew.

15.15 **Pharmacokinetic information:**
Absorption: Rapid
Metabolism: Approximately two-thirds of Lenalidomide is eliminated unchanged through urinary excretion.
Protein binding: ~30%
Time to peak, plasma: Healthy volunteers: 0.6-1.5 hours; Myeloma patients: 0.5-4 hours
Half-life elimination: ~3 hours
Excretion: Urine (~67% as unchanged drug)

15.16 **Potential Drug Interactions:**
Increased Effect/Toxicity: Abatacept and Anakinra may increase the risk of serious infection when used in combination with Lenalidomide. Lenalidomide may increase the risk of infections associated with vaccines (live organism).
Decreased Effect: Lenalidomide may decrease the effect of vaccines (dead organisms).
Herb/Nutraceutical Interactions: Avoid echinacea (has immunostimulant properties; consider therapy modifications).

15.17 **Known potential adverse events:** Consult the package insert for the most current and complete information.

Boxed Warnings:

1. Potential for human birth defects

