Melena, Mallory-Weiss syndrome, upper gastrointestinal hemorrhage, mucosal hemorrhage, hyperbilirubinemia, blood bilirubin increased, transaminases increased, blood alkaline phosphates increased, liver function test abnormal, basil cell carcinoma, dysesthesia, areflexia, motor dysfunction, sensory disturbance, burning sensation, muscle atrophy, blood urea increased, creatinine renal clearance decreased, oliguria, glomerular filtration rate decreased, renal tubular necrosis, acute prerenal failure, azotemia, pneumonitis, interstitial lung disease, pruritis generalized, angioedema, urticarial, eyelid edema,

Frequency not defined:

Hepatitis, hepatitis B viral reactivation, tumor lysis syndrome, squamous cell carcinoma of skin, eye swelling, periorbital edema, lip swelling, swollen tongue, mouth edema, pharyngeal edema, Stevens-Johnson syndrome, toxic epidermal necrolysis, drug reaction with eosinophilia and systemic symptoms (DRESS)

All study participants must be registered into the mandatory POMALYST REMSTM program, and be willing and able to comply with the requirements of the POMALYST REMSTM program. Females of reproductive potential must adhere to the scheduled pregnancy testing. Females of childbearing potential should not handle or administer pomalidomide unless they are wearing gloves.

15.28 **Drug procurement:** Commercial supplies. Pharmacies or clinics shall obtain supplies from normal commercial supply chain or wholesaler.

Per the standard POMALYST REMSTM program requirements, all physicians who prescribe pomalidomide for research subjects enrolled into this trial, and all research subjects enrolled into this trial, must be registered in and must comply with all requirements of the POMALYST REMSTM program.

15.29 **Nursing Guidelines**

15.259 Agent is known to be teratogenic in rabbits. Therefore all women who are pregnant or who could become pregnant, should not handle the agent

outside of the original packaging. Chemotherapy gloves should be worn if contact is necessary.

- 15.260 Because of the similarity of this agent to thalidomide certain precautions MUST be employed by all subjects on protocol and for 4 weeks after discontinuation of agent. Instruct patients the following must be adhered to: No donation of tissue/blood/semen/sperm; sexually active males/females must use protocol-specific contraception (regardless of fertility status-i.e. history of vasectomy).

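### The protocol's own pregnancy test is timed to registration and can be 35 days old at first dose; the entry criterion on drug-safety programs names pomalidomide's for cohorts listed only for lenalidomide

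*Combined protocol and SAP*

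**What the plan says.** **Test timing.** Inclusion criterion 3.18 requires a "Negative pregnancy test done ≤ 7 days prior to registration, for persons of childbearing potential only". Footnote 1 to the Section 4.0 Test Schedule repeats the anchor: "Must be done ≤ 7 days prior to registration". The pregnancy row has one entry, before registration, and none before Cycle 1 Day 1 or later. Section 6.5 then says: "Treatment cannot begin prior to registration and must begin ≤ 28 days after registration".

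**Testing under the programs.** Section 15 adds a second layer. For lenalidomide, 15.12 and 15.18 both state that "pregnancy testing is required for females of childbearing potential". For pomalidomide, 15.27 says: "Females of reproductive potential must adhere to the scheduled pregnancy testing". None of these gives an interval between the test and the first dose.

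**Which program.** Inclusion criterion 3.19c reads: "Willing to follow the requirements of the Pomalyst® REMS program". It applies to all cohorts. Sections 15.27 and 15.28 extend pomalidomide REMS registration to everyone in the trial, and 15.199e repeats it for all patients. For Cohorts A and B in Cycle 1, however, Section 7.1 says: "Patient may receive Lenalidomide OR Lenalidomide + Dexamethasone". In Cycles 2-6 their regimen must still be lenalidomide-based. Pomalidomide is listed only for Cohorts C and D, as an alternative to lenalidomide. Enrolment in the lenalidomide REMS is required by 15.18 and 15.201, but no criterion in Section 3 mentions it.

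**The concern.** An entry pregnancy test for a teratogenic drug is there to establish status when exposure begins. The protocol treats the hazard as serious: 3.21 excludes pregnant persons and those unwilling to use contraception, and 15.17 puts birth defects first among the lenalidomide boxed warnings. A window counted back from registration, followed by a start window of four weeks, does not by itself ensure a recent negative result at first dose. A coordinator working from Sections 3, 4 and 6 could satisfy every calendar rule with an old test.

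The second matter is one of eligibility wording. Section 13.4 makes a patient ineligible if any single criterion is not met. Read literally, a Cohort A or B patient must accept the program of a drug that 7.1 does not list for them, while Section 3 does not ask about the program that supplies their own drug.

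**Working it through.** **Age of the calendar test at first dose**

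Inputs:
- t = days from test to registration, 0 to 7 (3.18; Section 4.0 footnote 1).
- s = days from registration to first dose, 0 to 28 (6.5).

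Formula: age at first dose = t + s.

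- Minimum: 0 + 0 = 0 days.
- Maximum: 7 + 28 = 35 days.

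The calendar entry sits in the column for 14 days or less before registration. That column alone would give 14 + 28 = 42 days, but footnote 1 tightens it to 7 days, so 35 is the right maximum. The protocol states no figure of its own for the age of the test at first dose.

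If the same 7 days were counted back from Cycle 1 Day 1, the maximum would fall from 35 to 7 days. The 7 days is the protocol's own window moved to a new anchor. It is not taken from any REMS document.

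The 35 days is the age of the calendar test, not of the last test before exposure. The second quantity depends on the REMS schedule, which the protocol does not reproduce.

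**Patients tied to the pomalidomide REMS without pomalidomide being listed for them**

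Inputs, from 16.22: maximum accrual A 32, B 32, C 63, D 63, total 190.

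- Cohorts A and B: 32 + 32 = 64.
- Share of planned accrual: 64 / 190 = 33.7%.

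**REMS requirements by section**

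| Section | Program | Applies to |
|---|---|---|
| 3.19c | Pomalidomide | All patients, as an entry criterion |
| 15.27, 15.28, 15.199e | Pomalidomide | All patients |
| 15.18, 15.201 | Lenalidomide | Patients supplied with lenalidomide |
| Section 3 | Lenalidomide | Not mentioned |

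For Cohorts A and B, the program their drug needs is required in Section 15 but absent from Section 3. The program named in Section 3 belongs to a drug that 7.1 does not list for them.

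**The case against.** The strongest reply is that the restricted-distribution programs already do this work. Sections 15.12 and 15.18 place pregnancy testing in the same rule as the 28-day supply limit and the new prescription for each fill, and no first dose can be taken without dispensing. On that view the calendar test is only an eligibility screen. The protocol leaves all testing in Cycles 2-6 to the programs, so it could do the same at Cycle 1. Sections 3.21 and 15.193 add contraception requirements.

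Much of this stands. A reader might infer from the 35 days that patients can begin treatment with no more recent test. The documents do not support that, because program testing is required as well. It is also fair that on-treatment testing is left to the programs, and this point does not challenge that. What does not stand is the idea that the programs settle the timing within this protocol: Section 15 states no interval to first dose. At entry, unlike in later cycles, the protocol sets its own test and its own window, and that window is counted from the wrong event.

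On the second matter, a reader might infer that lenalidomide patients are under no REMS requirement. That is also unsupported: 15.18 and 15.201 make enrolment mandatory. What remains is that 3.19c disagrees with Sections 7 and 15. It might be said that 15.199e, being in the pomalidomide nursing guidelines, is meant only for recipients of that drug. That reading is open for 15.199e, but 15.27 and 15.28 expressly reach everyone enrolled.

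**Conclusion.** Both parts hold, and both are minor. No endpoint, estimate or analysis is affected.

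- **Test timing: a cheap improvement.** The calendar test can be up to 35 days old at first dose. The actual risk is probably low, given the program testing in Section 15. It cannot be sized, because the documents give neither the distribution of start days nor the number of patients of childbearing potential. The median age at onset of 65-70 years in Section 1.0 suggests the number is small.
- **REMS wording: wrong as written for Cohorts A and B.** Sections 3.19c, 15.27, 15.28 and 15.199e apply the pomalidomide program to 64 of 190 planned patients (33.7%) for whom 7.1 lists only lenalidomide. The 64 counts patients subject to the misdirected wording. It is not a count of patients harmed or left without a program.

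The first part assumes the windows in 3.18 and 6.5 are used to their limits. The second assumes accrual reaches the maximum in 16.22.

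**What to change.** 1. Reword 3.18 and Section 4.0 footnote 1 to require a negative test no more than 7 days before Cycle 1 Day 1 for persons of childbearing potential, repeated if the start slips beyond that window.
2. Mark the pregnancy row in the existing calendar column before Cycle 1 Day 1, without footnote 3 ("Baseline then only if clinically indicated"), so that the test is not discretionary.
3. State that a REMS test done within the same 7 days counts.
4. Reword 3.19c to refer to the REMS program of the immunomodulator to be given, whether lenalidomide or pomalidomide.
5. Limit 15.27, 15.28 and 15.199e to patients who receive pomalidomide.

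The cost is wording in five sections and the calendar (one footnote, one cell). Some patients of childbearing potential will need a repeat pregnancy test when the registration test has aged out and no program test falls in the window. This may sometimes mean a separate visit: apart from the medication diary, every entry in that pre-treatment column carries footnote 3, so a visit just before Cycle 1 is not guaranteed.

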3.2 Registration - Exclusion Criteria

3.21 An agent that has known genotoxic, mutagenic and teratogenic effects:

- Pregnant persons
- Nursing persons
- Persons of childbearing potential who are unwilling to employ adequate contraception

3.22 Co-morbid systemic illnesses or other severe concurrent disease which, in the judgment of the investigator, would make the patient inappropriate for entry into this study or interfere significantly with the proper assessment of safety and toxicity of the prescribed regimens.

3.23 Immunocompromised patients and patients known to be HIV positive and currently receiving antiretroviral therapy.

3.24 Uncontrolled intercurrent illness including, but not limited to, ongoing or active infection, symptomatic congestive heart failure, unstable angina pectoris, cardiac arrhythmia, or psychiatric illness/social situations that would limit compliance with study requirements.

3.25 Receiving any other investigational agent which would be considered as a treatment for the primary neoplasm.

3.26 History of myocardial infarction ≤ 6 months.

4.0 Test Schedule

Tests and procedures	Active Monitoring Phase					
	Prior to registration		Prior to Day 1 Cycle 1	Prior to Day 1 Cycle 2	Prior to Day 1 Cycles 3-6	End of Treatment
	≤28 days	≤14 days				
Window				±3 days	±3 days	±7 days
Complete Medical History		X				
Physical exam, Wt, PS		X	X ³	X	X	X
Adverse event assessment		X		X	X	X
Pregnancy test ¹		X				
Height		X				
Hematology group: CBC with 5-part differential		X	X ³	X	X	X
Chemistry group to include serum creatinine, calcium, T.Bili, D. bili, AST, and ALT		X	X ³	X	X	X
LDH, Beta-2-microglobulin, Plasma cell assessment		X	X ³			
PT/PTT/INR		X				
TSH		X				
Electrophoresis of serum and urine		X	X ^{3,5}	X ⁵	X ⁵	X ⁵
Immunofixation or mass fixation of serum and urine		X		X ⁷	X ⁷	X ⁷
Affected Serum Immunoglobulin ²		X	X ³	X	X	X
Serum Immunoglobulin free light chain		X	X ³	X	X	X
WBLDCT ³ or PET/CT	X			X ³	X ³	
Bone marrow aspirate and biopsy	X					
Patient Medication Diary (Appendix II)			X	X	X	
Research bone marrow sample ^R	X			X ⁶		X ⁴
Research blood sample ^R	X			X ⁶		X ⁴

Cycle 1 = 21

Cycles 2-6 = 28 days

Footnotes on following page:

1. For women of childbearing potential only. Must be done ≤ 7 days prior to registration. If the urine test is positive or cannot be confirmed as negative, a serum pregnancy test will be required
2. Affected immunoglobulin refers to the baseline M-protein type, that is, IgG, IgA, or IgD. Not applicable if patient “non-secretory” or if patient has no heavy chain, i.e. light chain myeloma. Affected immunoglobulin is required after baseline only if it used for disease monitoring instead of SPEP (e.g. IgA myeloma).
3. Baseline then only if clinically indicated.
4. Optional BM sample submission for patients who discontinue treatment due to disease progression or relapse, intolerable AEs, patient refusal, subsequent treatment for myeloma.
5. Urine Electrophoresis required only if used to assess disease response
6. Bone marrow aspirate done at the end of Cycle 1 (prior to cycle 2) will be paid for by research.
7. Immunofixation (IF) only needed in absence of M-Spike to document CR or SCR

R Collected as part of the IRB# 521-93, IRB# 14-009163 and/or IRB# 919-04

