1.2 Rationale for the current trial

Current treatment regimens in both the upfront and relapsed settings have trended towards utilizing combination therapies that include a combination of an IMiD with proteasome inhibitors and/or monoclonal antibodies(21, 22). This is largely due to the results of several phase III clinical trials demonstrating the overall benefit of three-drug regimens (triplets) containing IMiDs and proteasome inhibitors or IMiDs and monoclonal antibodies over two-drug regimens (doublets) containing IMiDs alone with dexamethasone in terms of their depth and duration of hematological response. However, some patients within these clinical trials as well as in real-world clinical practice may derive equal depth and duration of therapeutic response to two-drug regimens (doublets) containing IMiDs alone with dexamethasone compared to triplets. At this time, our gap in knowledge prevents us from *apriori* identifying those patients who can be spared the physical and financial toxicity of adding the additional third or fourth agent such as proteasome inhibitors and/or monoclonal antibodies to an IMiD and dexamethasone. Being able to develop and validate biomarkers capable of filling this fundamental gap of knowledge could have practical implications to the clinical care of patients with MM. **As such, this study will provide the possibility of obtaining biospecimens from untreated smoldering MM and MM patients as well as previously treated MM patients pre- and post-treatment with one cycle of therapy containing only an IMiD and dexamethasone.**

Furthermore, it has been long hypothesized that there may be a differential response to IMiDs for patients belonging to African American (AA) race. Small studies have suggested that AA patients may have a better response to IMiDs than whites but receive a lesser access to these agents. This has led to the need for a more definitive testing to develop an efficacy profile as well as biomarker identification which may help predict the differences in response among AA and white patients with MM.

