3.0 Registration Patient Eligibility

3.1 Registration - Inclusion Criteria

3.11 Age \geq 18 years

3.12 **Cohort A:** Patient must have untreated smoldering multiple myeloma which is defined by the presence of 10% or more but less than 60% clonal plasma cells in the bone marrow and the absence of any of the following myeloma related symptoms or laboratory and radiographic abnormalities: anemia, hypercalcemia, renal insufficiency, hypercalcemia, serum free light chain ratio of greater than 100 or more than one focal marrow multiple myeloma lesion on MRI imaging.

Cohort B: Patient must have newly diagnosed myeloma requiring treatment and no prior therapies

Cohort C: Patient must have relapsed or refractory multiple myeloma with at least one prior therapy for their multiple myeloma but not refractory to all IMiDs

Cohort D: Patient must have relapsed or refractory multiple myeloma with Lenalidomide as part of a maintenance regimen as their most recent therapy

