14.3 Metabolomics profiling

To determine if specific metabolite profiles within the bone marrow and peripheral blood plasma will be reflective of the metabolic phenotype within the clonal bone marrow plasma cells that predict for response to therapy with an IMiD.

Methodology: For this analysis, bone marrow and peripheral blood plasma will undergo large scale, untargeted metabolite profiling via liquid chromatography mass spectrometry. Differentially expressed metabolites in responder versus non-responders will be evaluated for the development of a potential biomarker predicting clinical response.

Sample type and timing: Bone marrow aspirate samples will be collected in (1) 5 ml EDTA (purple top) tube and placed on ice or a cool pack. Samples to be collected prior to cycle 1 and then prior to cycle 2.

Sample Destination:

[name]
Mayo Foundation
[name]
[name]

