16.0 Statistical Considerations and Methodology

16.1 Overview:

This is a pilot study to determine the response rates (>PR) of the combination of an immunomodulator and dexamethasone in Multiple Myeloma (MM) patients of each clinically relevant biomarker. This combination will be evaluated in four cohorts: Cohort A (Smoldering MM), Cohort B (Newly Diagnosed MM), Cohort C (Relapsed/Refractory MM) and Cohort D (Relapsed on Len maintenance). This study will not utilize a formal statistical design but will focus more on estimation rather than hypothesis testing.

16.11 Primary Endpoint: The primary endpoint of this trial is to estimate (>PR) response rates (RR) after one cycle of treatment. Biomarkers of interest will be identified and categorized into clinically relevant groups (e.g. positive vs. negative) by evaluating baseline and post treatment (after cycle one) biospecimens. RR will be estimated within each biomarker.

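### Baseline research marrow and blood in Cohorts C and D may be drawn on or off the previous drug, and the biomarker analyses neither record nor adjust for which

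*Combined protocol and SAP*

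**What the plan says.** **Timing of the draw.** The Section 4.0 schedule has rows for "Research bone marrow sample" and "Research blood sample". In both, the only mark before treatment is in the column for 28 days or less before registration. The column for the period just before Day 1 of Cycle 1 is empty. Section 6.5 adds: "Treatment cannot begin prior to registration and must begin ≤ 28 days after registration".

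Section 14 words the timing differently. Table 14.1 marks the draw simply as before Day 1 of Cycle 1, 14.3 says "Samples to be collected prior to cycle 1 and then prior to cycle 2", and 14.4 agrees with 14.3.

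**Who is sampled.** Cohort C has had at least one prior therapy. The Cohort D criterion reads: "Patient must have relapsed or refractory multiple myeloma with Lenalidomide as part of a maintenance regimen as their most recent therapy". Section 5.1 labels that cohort as relapsed on lenalidomide maintenance. Section 3 sets no interval since the last therapy, and the concurrent-treatment exclusion in 3.25 covers investigational agents only.

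**How the specimens are used.** Section 1.2 describes sampling "previously treated MM patients pre- and post-treatment with one cycle of therapy containing only an IMiD and dexamethasone". Section 16.11 forms the marker groups "by evaluating baseline and post treatment (after cycle one) biospecimens". Sections 16.321 and 16.323 relate markers to response by logistic regression and, in 16.323, also chi-square or Fisher tests. Neither includes a term for drug status at the draw. The only prior-therapy item among the Section 12 descriptive factors is the number of prior treatments.

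**The concern.** The planned assays are untargeted metabolomics of marrow and blood plasma, plus genomics, transcriptomics and intracellular metabolomics of the myeloma cells. Readouts of this kind can plausibly move with a drug the patient is taking. If some patients in a cohort are sampled on their previous drug and others off it, a marker may differ between them for that reason alone. If response also differs between the same two groups, the marker will look associated with response without carrying information about the tumour. Analysing each cohort separately removes such mixing between cohorts, but not within C or within D.

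The change from before to after Cycle 1 raises a separate problem. For a Cohort D patient still taking lenalidomide at the first draw, the comparison is between two IMiD-exposed specimens, not between a specimen free of the drug and one taken after it.

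**Working it through.** **1. Timing.** 28 days (4.0, before registration) + 28 days (6.5, registration to treatment) = 56 days at most between the baseline draw and Cycle 1 Day 1.

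**2. Patients in scope.** Section 16.22 gives 32 + 32 + 63 + 63 = 190, which reproduces the stated maximum accrual. Cohorts C and D are 63 + 63 = 126, and 126/190 = 66%. Among evaluable patients, (60 + 60)/(30 + 30 + 60 + 60) = 120/180 = 67%.

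**3. Search for an off-therapy condition or a recorded status.**

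| Section | Off previous therapy at the draw? | On/off status used? |
|---|---|---|
| 3.1, 3.2 | No; 3.25 reaches investigational agents only | – |
| 4.0 | No | – |
| 12 | – | No; number of prior treatments only |
| 14.1, 14.3, 14.4 | No; only before Cycle 1 | – |
| 16.321, 16.323 | – | No |

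**4. How a null marker acquires an association.** Every input here is an assumption; the documents give none of them. Let *f* be the share on drug at the draw, *m* the marker-positive proportion and *r* the response rate in each status group, with marker and response independent within each group. Then

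- P(M+) = *f*·m_on + (1 − *f*)·m_off
- RR in M+ = [*f*·m_on·r_on + (1 − *f*)·m_off·r_off] / P(M+)
- RR in M− = [*f*·(1 − m_on)·r_on + (1 − *f*)·(1 − m_off)·r_off] / [1 − P(M+)]

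With *f* = 0.5, m = 0.2 on and 0.8 off, r = 0.3 on and 0.5 off:

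- P(M+) = 0.10 + 0.40 = 0.50
- RR in M+ = (0.03 + 0.20)/0.50 = 0.46
- RR in M− = (0.12 + 0.05)/0.50 = 0.34
- Odds ratio = (0.46/0.54)/(0.34/0.66) = 1.65, where the true within-group value is 1

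Over *f* = 0.3 to 0.7 and n = 60:

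| Response on v off | Marker positive on v off | Crude odds ratio | Chance of nominal p < 0.05 |
|---|---|---|---|
| 40% v 40% | either setting below | 1.0 | 5% |
| 30% v 50% | 40% v 60% | 1.15–1.18 | about 5% |
| 30% v 50% | 20% v 80% | 1.55–1.65 | 12–15% |
| 20% v 60% | 40% v 60% | 1.31–1.40 | 8–9% |
| 20% v 60% | 20% v 80% | 2.4–2.8 | 36–47% |

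**5. Continuous marker.** This is a logistic likelihood-ratio simulation with n = 60 and a null marker shifted 0.5 to 1.2 SD by the drug. Ranges cover repeat simulations of 1,500 and 3,000 runs per setting, with half the patients on drug.

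| Response on v off | Positive at nominal 5% |
|---|---|
| 25% v 40% (gap 15 points) | 6–11% |
| 20% v 45% (gap 25 points) | 9–21% |
| 15% v 50% (gap 35 points) | 11–35% |
| equal | 5–6% |

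With 90% on drug, the three unequal settings give about 6–12%. With an on/off term in the model, the rate returns to about 5–6.5%.

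**The case against.** The strongest reply is that the mechanism is only conditional, and may be weak in Cohort D. Section 5.1 describes the whole cohort as relapsed on lenalidomide maintenance. If that is literally so, on/off status at the draw may reflect little more than scheduling, and no document ties it to response. The eligibility wording asks only that such maintenance be the most recent therapy, so it could admit patients who had already stopped, but nothing says how many. In Cohort C the previous drug can be any regimen, so one common marker shift is a simplification. This stands: the inflation figures illustrate what can happen and do not predict what will.

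The study is also a pilot centred on estimation, and Secondary Goal 1, which speaks of prediction, names untreated patients. This stands only in part. Goal 3 covers previously treated patients, 16.321 is not restricted to Cohorts A and B, and confounding distorts an estimate as readily as a test.

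Collection runs under separate IRB protocols that are not in the documents and may set conditions for the draw. That is possible, but it would not put the missing term into the Section 16 analyses.

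A reader might also go further in two ways that the documents do not support:

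- **That the plan passes these specimens off as untreated.** Section 1.2 expressly calls the patients previously treated, and 16.11 speaks only of baseline.
- **That the problem could never be repaired.** Section 12 is a list of descriptive factors, not an inventory of the case report forms, which are not in the documents. The medical history required by 4.0 or the relapse documents required by 18.5 may hold the last-dose date. What can be said is that no listed factor captures it.

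**Conclusion.** The gap is real and the consequence conditional. As written, the plan allows on-drug and off-drug baselines to be mixed within Cohorts C and D, two-thirds of projected accrual, and gives the analysis no means of separating them. A spurious association needs status to vary within a cohort and to be related to both marker and response. If all three hold at the assumed sizes in step 5, a nominal 5% test is positive about 6 to 35% of the time. If response does not differ by status the rate is near 5 to 6%, and if nearly all patients are on drug the inflation is smaller. It would be wrong to quote any of these as the study's false-positive rate, because the split, the response gaps and the marker shift are all assumed.

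The pre/post problem in Cohort D does not depend on a link with response. It arises whenever a patient is still taking lenalidomide at the first draw. No sample size or accrual figure changes. This is a low-cost improvement to the plan, not a flaw that invalidates it.

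**What to change.** 1. **Section 12:** add, for Cohorts C and D, the last-dose date of the previous regimen and on/off-drug status at the baseline research draw.
2. **Sections 16.321 and 16.323, Cohorts C and D:** include that status as a covariate and repeat each analysis on off-drug specimens only. Report any pre/post change separately by status.
3. **Sections 4.0 and 14.1:** reconcile the stated time of the baseline draw and keep marrow and blood paired. Moving only the blood to the start of treatment would separate it from the marrow that 14.3 profiles alongside it, and would leave the marrow possibly on drug.

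No washout, dose or treatment-stopping rule is proposed. When previous therapy stops remains a clinical decision; only the record and the analysis change.

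The cost is a small addition to the data collected (a date, from which status follows), one model term, and a sensitivity set smaller than the full cohort. If almost all patients in a cohort share one status, the covariate will be poorly estimated. Reporting the split then becomes the main benefit.
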